2.8.2.9 Genotyping

Exploratory models will be fitted to investigate the correlation between genotype expression and visual acuity and dry retina. Analyses relating to genotype expression will be planned in an independent Statistical Methods document, and will also be reported independently.

2.8.2.10 Time to Event

Time to event analyses will be conducted using Kaplan Meier. Cox Hazards analysis may also be used as deemed appropriate.

2.9 Safety evaluation

Safety parameters will include adverse events, the results of ophthalmic examinations, IOP, vital signs, and laboratory results if reported as AE.

All safety analyses will be conducted within the Safety Set.

2.9.1 Adverse events

Adverse events (AEs) will be reported by primary system organ class and preferred term according to the Medical Dictionary for Regulatory Activities (MedDRA).

The MedDRA version used for reporting the study will be described in a footnote.

AEs will be deemed treatment emergent if the onset date is on or after the date of first study treatment. Any AEs recorded prior to the start of study treatment will be listed together with all other AEs. If any event has an incomplete onset date, this will be handled as described in section 2.4.3.1 above.

The incidence of treatment emergent AEs will be summarized separately for ocular and non-ocular AEs as follows:

- All AEs
- AEs by maximum severity
- AEs suspected to be related to study drug
- Serious AEs
- AEs leading to study treatment discontinuation

Patients who experienced multiple adverse events for a preferred term will be counted once, similarly for patients with multiple adverse events per system organ class.

All information pertaining to AEs noted during the study will be listed by patient, detailing AE (e.g., verbatim given by the investigator as well as the system organ class and preferred term according to MedDRA), date of starting and ending, severity, suspected relationship (by the investigator) to the study drug / ocular injection, and eye (for ocular events). The AE onset will also be shown relative (in number of days) to the day of (first) initial study treatment (ranibizumab injection) and relative (in number of days) to the Day 1.

The following AE listings will be provided:

- All adverse events,
- Ocular adverse events
- Adverse events suspected to be related to study drug and/or ocular injection.
- Serious adverse events,
- Adverse events leading to treatment withdrawal
- Adverse events leading to treatment interruption

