**Tables (Section 14.3.1)**

**Table 14.3.1-1 Incidence of adverse events, regardless of study drug relationship, by primary system organ class, preferred term and treatment**

Safety Set

| System Organ Class (SOC)
Preferred Term (PT) | Intensive
(N=X)    |              | Relaxed
(N=X)      |              | Total
(N=X)        |              |
|---|-----------------------|--------------|-----------------------|--------------|-----------------------|--------------|
|   | Nr (%) of
Subjects | Nr of
AEs | Nr (%) of
Subjects | Nr of
AEs | Nr (%) of
Subjects | Nr of
AEs |
| All Body Systems                                | x (xx.x%)             | x            | x (xx.x%)             | x            | x (xx.x%)             | x            |
| SOC1  | x (xx.x%)             | x            | x (xx.x%)             | x            | x (xx.x%)             | x            |
| PT1   | x (xx.x%)             | x            | x (xx.x%)             | x            | x (xx.x%)             | x            |
| PT2   | x (xx.x%)             | x            | x (xx.x%)             | x            | x (xx.x%)             | x            |
| ....  | ....                  | ....         | ....                  | ....         | ....                  | ....         |
| PTx   | x (xx.x%)             | x            | x (xx.x%)             | x            | x (xx.x%)             | x            |
| SOC2  | x (xx.x%)             | x            | x (xx.x%)             | x            | x (xx.x%)             | x            |
| PT1   | x (xx.x%)             | x            | x (xx.x%)             | x            | x (xx.x%)             | x            |
| PT2   | x (xx.x%)             | x            | x (xx.x%)             | x            | x (xx.x%)             | x            |
| ....  | ....                  | ....         | ....                  | ....         | ....                  | ....         |
| PTx   | x (xx.x%)             | x            | x (xx.x%)             | x            | x (xx.x%)             | x            |

.....  
AE: Adverse Event

Note: Multiple records from the same subject are only counted once within the same category

**Table 14.3.1-2 Incidence of ocular adverse events, regardless of study drug relationship, by primary system organ class, preferred term and treatment**

Safety Set

| System Organ Class (SOC)
Preferred Term (PT) | Intensive
(N=X)    |              | Relaxed
(N=X)      |              | Total
(N=X)        |              |

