**Listing 16.2.5-2 Dose administration record by treatment (FELLOW eye)**

**Safety Set**

| Subject Number | Visit         | Was treatment for FELLOW eye given? | FELLOW eye treated | Date of dosing (YYYY-MM-DD) | Treatment for wet AMD to fellow eye | Total dose administered |
|----------------|---------------|-------------------------------------|--------------------|-----------------------------|-------------------------------------|-------------------------|
| XXX-XX         | Baseline      | Yes                                 | Left eye           | YYYY-MM-DD                  | xxxxxxxxxxxxx                       | XX units                |
|                | Week n | Yes                                 | Left eye           | YYYY-MM-DD                  | Not xxxxxxxxxxxxx                   | XX units                |
|                | .....         |                                     |                    |                             |                                     |                         |
| XXX-XX         | Baseline      | Yes                                 | Right eye          | YYYY-MM-DD                  | xxxxxxxxxxxxx                       | XX units                |
|                | Week n | No                                  | -                  | -                           |                                     | -                       |
|                | .....         |                                     |                    |                             |                                     |                         |

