Table 2-1	Analysis set exclusion summary	8
Table 2.3-3	Study Assessment Windows	9
Table 2.7.2-1	Primary Efficacy Analyses.....	23
Table 2.7.2-2	Secondary Efficacy Analyses.....	23
Table 2.7.2-3	Exploratory Efficacy Analyses	23
Table 2.7.2.5-1	Mixed Models	26
Table 2.7.2.8-1	Logistic Regression Models.....	28

1 Introduction

[figure not shown]
Studies covered are listed in Table 1-1. The study design, objective, treatment duration, and efficacy variables for this indication may be different from other related studies due to different indications and phases of clinical development so that almost every study is unique. The main purpose is to provide project-level standards for the statistical analyses of efficacy and safety data which are common or similar across studies. This MAP can be used as a reference or guidance of statistical methods for future studies not listed in Table 1-1.

Table 1-1 Studies covered in the MAP

Indication /Study	Phase/ Duration	Treatment/ dose	Primary objective
AMD / RFB002	IV	(1) Intensive retinal fluid retreatment regimen (2) Relaxed retinal fluid retreatment regimen	To test the non-inferiority (visual acuity benefit that is not clinically worse) of intravitreal ranibizumab when administered to resolve IRF or SRF >200 µm under the fovea (relaxed retinal fluid management) relative to when administered to completely resolve both IRF and SRF (intensive retinal fluid management) in patients with wet AMD. The primary endpoint for the study will be the mean change in BCVA from baseline to month 24.

This is a randomised, multi-centre, non-inferiority trial investigating a relaxed fluid retreatment regimen relative to an intensive fluid retreatment regimen (using a non-inferiority margin of 5 letters on the primary endpoint of mean change in BCVA). After consenting to participate in the study, patients will participate in a screening period lasting up to 2 weeks to evaluate patient eligibility. After eligibility confirmation at the Baseline Visit, patients will be randomised in a 1:1 ratio to one of the two treatment arms i.e. intensive retinal fluid regimen or relaxed retinal fluid regimen within the appropriate stratum depending on the treatment at baseline for the non-study eye i.e. none, ranibizumab or other anti-VEGF therapy. Only one eye will be selected/treated as the study eye.

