2.1 General considerations

Descriptive statistics will include n (number of observations), mean, standard deviation, median, minimum and maximum for continuous variables, and frequencies and percentages for categorical variables.

The study eye is the eye identified by the investigator according to the protocol inclusion and exclusion criteria and recorded as such at the screening visit in the eCRF.

The efficacy analyses of this study will be based on the study eye data only.

For non-ocular, study eye, and fellow eye summary tables, figures, and listings will be based on all patients included in the analysis/set population under consideration. Unless otherwise specified, all confidence intervals (CIs) and p values will be two-sided and will be based on an alpha significance level of 0.05.

Central Reading Centre data will be used for efficacy summary tables and analyses, whilst all site and Central Reading Centre data will be included in listings.

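### The ocular adverse-event tables do not separate study eye from fellow eye, so fellow-eye events enter the comparison of the two regimens

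*SAP*

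**What the plan says.** **Allocation and eye.** SAP section 1 says that "patients will be randomised in a 1:1 ratio to one of the two treatment arms" and that "Only one eye will be selected/treated as the study eye". Randomisation is stratified "depending on the treatment at baseline for the non-study eye i.e. none, ranibizumab or other anti-VEGF therapy". Fellow-eye treatment is also recorded by visit during the study: Listing 16.2.5-2 has a column headed "Treatment for wet AMD to fellow eye".

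**Adverse events.** SAP 2.9.1: "The incidence of treatment emergent AEs will be summarized separately for ocular and non-ocular AEs as follows". The items that follow (all events, maximum severity, suspected relationship, serious, leading to discontinuation) do not mention study eye or fellow eye. A patient counts once per preferred term and once per system organ class. The eye is to be shown in the listings.

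**Table shells** (the document supplied as the Protocol). Table 14.3.1-2 is titled "Incidence of ocular adverse events, regardless of study drug relationship, by primary system organ class, preferred term and treatment". It and the other ocular tables (14.3.1-4, -7, -9, -11, -13 and -15) group results as Intensive, Relaxed and Total. None has a row, column or footnote for the eye. Listing 16.2.7-2 gives the site as left, right or both, not as study or fellow.

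**Elsewhere in the SAP.** Section 2.1 refers to such outputs in general ("For non-ocular, study eye, and fellow eye summary tables, figures, and listings") but settles only which patients they are based on. Section 2.6 plans exposure summaries for injections in the study eye and in the treated fellow eye. Section 2.7 plans separate medication summaries for non-ocular use, study eye and fellow eye, with treatments given to both eyes entered under each.

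**The concern.** The randomised regimen governs retreatment of the study eye. A fellow eye may be having its own injections, with ranibizumab or another product, on a schedule that the allocation does not set. If its events are counted with those of the study eye, the ocular incidence by arm mixes events that the regimen can cause with events that largely reflect something else.

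Number of injections is a key secondary variable (SAP 2.8.1), so study-eye ocular events are the natural safety counterpart when the regimens are compared. Because a patient counts once per preferred term, someone with an event only in the fellow eye looks the same in these tables as someone with that event in the study eye. The listings do not repair this: each left or right entry has to be matched by hand to the patient's study-eye record, and a listing gives no incidence by arm.

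**Working it through.** The plan states no adverse-event rate, so it has no figure of its own to reproduce here. All rates below are hypothetical and show only direction and mechanism.

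**Event rates.** Set the relaxed study-eye rate to 1 and the intensive study-eye rate to 1.5. Let fellow eyes add f (as a fraction of the relaxed study-eye rate) in both arms.

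- Pooled ratio = (1.5 + f)/(1 + f).
- f = 0.25: 1.75/1.25 = 1.40.
- f = 0.50: 2.00/1.50 = 1.33.
- Pooled difference = (1.5 + f) − (1 + f) = 0.5 for every f.

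The ratio moves toward 1; the absolute rate difference does not change.

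**Patients with at least one event.** Let s be the study-eye risk and f now the fellow-eye risk, equal in both arms, with the two eyes independent. The pooled risk is 1 − (1 − s)(1 − f), so the pooled risk difference is (1 − f) times the study-eye difference.

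| Study eye, intensive vs relaxed | f | Pooled risks | Difference (points) | Risk ratio |
|---|---|---|---|---|
| 30% vs 20% | 0 | 30% vs 20% | 10.0 | 1.50 |
| 30% vs 20% | 10% | 37% vs 28% | 9.0 | 1.32 |
| 30% vs 20% | 20% | 44% vs 36% | 8.0 | 1.22 |
| 10% vs 5% | 0 | 10% vs 5% | 5.0 | 2.00 |
| 10% vs 5% | 10% | 19% vs 14.5% | 4.5 | 1.31 |
| 10% vs 5% | 20% | 28% vs 24% | 4.0 | 1.17 |

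The difference shrinks modestly. The ratio shrinks more, and most when study-eye events are uncommon relative to fellow-eye events. With f = 0 nothing changes.

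**Unequal fellow-eye risk.** Keep the study eye at 30% vs 20%, a true difference of 10 points.

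- Fellow eye 15% vs 5%: 1 − 0.70 × 0.85 = 40.5%, against 1 − 0.80 × 0.95 = 24.0%. The difference is 16.5 points.
- Fellow eye 5% vs 15%: 1 − 0.70 × 0.95 = 33.5%, against 1 − 0.80 × 0.85 = 32.0%. The difference is 1.5 points.

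So pooling dilutes when fellow-eye risk is balanced and can exaggerate or mask when it is not.

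**The case against.** **Pooling is inferred.** No sentence in the SAP says that both eyes are counted together, and 2.1 can be read as a convention covering all tables. The shells are also rough: six of the seven ocular tables carry an all-body-systems top row, and the medication shells (Tables 14.3-3 and 14.3-4) show no eye breakdown although 2.7 asks for one. A missing row in a shell is therefore weak evidence by itself. What remains is that for adverse events neither the SAP text nor any shell asks for the split, and 2.1 does not supply it.

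**Patient-level incidence is legitimate.** A reader might infer that only the study eye was randomised and that the planned tables are therefore invalid. The documents do not support this. The patient is the unit of allocation, and ocular incidence per patient is a fair comparison, only less specific to the regimen.

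**Mitigation.** Stratification on fellow-eye treatment should keep fellow-eye risk similar across arms. Tables 14.3.1-7, -11 and -13 are limited to events suspected to be drug-related or leading to withdrawal or interruption, which should remove many fellow-eye events. It need not remove all, since a fellow eye may also be receiving ranibizumab.

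**Size.** The adverse-event shells give counts and percentages, with no ratio, interval or test, so there is no planned test to lose power. A reader might take a frequency of fellow-eye treatment from the filled-in cells of Table 14.1-10 (84 of 347). Those cells should not be used: the same values recur under genotype-sample headings in Table 14.1-11, and columns of 252 and 95 do not fit 1:1 allocation. They also describe earlier exposure, not treatment during the study.

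**Unseen source.** The clinical study protocol that the SAP cites was not among the documents and may hold rules on how fellow-eye events are reported or attributed.

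**Conclusion.** The point holds as a gap in the specification of the safety tables. As written, SAP 2.9.1 and the seven ocular shells let fellow-eye events count in each regimen's ocular incidence, out of step with 2.1, 2.6 and 2.7. With balanced fellow-eye risk, the relative comparison is pulled toward 1; the absolute event-rate difference is unchanged, and the patient-level risk difference shrinks by the factor 1 minus the fellow-eye risk if the eyes are independent. With unbalanced risk the error can go in either direction.

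The size cannot be derived, because the documents give no ocular event rates for either eye. A reader might infer that the tables will hide a real safety difference, or that injection-related events are the main cost of intensive treatment; the documents establish neither. The effect is confined to descriptive safety output. Efficacy analyses use study-eye data only (SAP 2.1), so the primary comparison is untouched.

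**What to change.** In SAP 2.9.1, state that ocular adverse events and ocular serious adverse events will be tabulated separately for the study eye and the fellow eye, with events in both eyes counted in each, following the rule already used in 2.7. Name the study-eye table as the one from which the regimen comparison is read. An either-eye table may be kept beside it if labelled as such.

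Amend Tables 14.3.1-2, -4, -7, -9, -11, -13 and -15 to match, and reconcile 2.9.1 and the shells with 2.1. If space is short, the tables of all ocular events (14.3.1-2) and of serious ocular events (14.3.1-9) come first.

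The cost is additional table pages and a derivation linking the recorded eye to the study eye. No new data are needed.

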| SOC2  | x (xx.x%)          | x (xx.x%)             | x (xx.x%)           | x (xx.x%)         | x (xx.x%)             | x (xx.x%)           | x (xx.x%)         | x (xx.x%)             | x (xx.x%)           |
| PT1   | x (xx.x%)          | x (xx.x%)             | x (xx.x%)           | x (xx.x%)         | x (xx.x%)             | x (xx.x%)           | x (xx.x%)         | x (xx.x%)             | x (xx.x%)           |
| PT2   | x (xx.x%)          | x (xx.x%)             | x (xx.x%)           | x (xx.x%)         | x (xx.x%)             | x (xx.x%)           | x (xx.x%)         | x (xx.x%)             | x (xx.x%)           |
| ....  | x (xx.x%)          | x (xx.x%)             | x (xx.x%)           | x (xx.x%)         | x (xx.x%)             | x (xx.x%)           | x (xx.x%)         | x (xx.x%)             | x (xx.x%)           |
| PTx   | x (xx.x%)          | x (xx.x%)             | x (xx.x%)           | x (xx.x%)         | x (xx.x%)             | x (xx.x%)           | x (xx.x%)         | x (xx.x%)             | x (xx.x%)           |

Note: Subjects are counted once at maximum severity within each sub grouping.

**Table 14.3.1-5 Incidence of adverse events, by primary system organ class, preferred term, maximum relationship to study drug and treatment**

Safety Set

| System Organ Class (SOC)
Preferred Term (PT) | Intensive
(N=X) |           | Relaxed
(N=X) |           | Total
(N=X) |           |
|---|--------------------|-----------|------------------|-----------|----------------|-----------|
|   | Not Suspected      | Suspected | Not Suspected    | Suspected | Not Related    | Related*  |
| All Body Systems                                | x (xx.x%)          | x (xx.x%) | x (xx.x%)        | x (xx.x%) | x (xx.x%)      | x (xx.x%) |
| SOC1  | x (xx.x%)          | x (xx.x%) | x (xx.x%)        | x (xx.x%) | x (xx.x%)      | x (xx.x%) |
| PT1   | x (xx.x%)          | x (xx.x%) | x (xx.x%)        | x (xx.x%) | x (xx.x%)      | x (xx.x%) |
| PT2   | x (xx.x%)          | x (xx.x%) | x (xx.x%)        | x (xx.x%) | x (xx.x%)      | x (xx.x%) |
| ....  | x (xx.x%)          | x (xx.x%) | x (xx.x%)        | x (xx.x%) | x (xx.x%)      | x (xx.x%) |
| PTx   | x (xx.x%)          | x (xx.x%) | x (xx.x%)        | x (xx.x%) | x (xx.x%)      | x (xx.x%) |
| SOC2  | x (xx.x%)          | x (xx.x%) | x (xx.x%)        | x (xx.x%) | x (xx.x%)      | x (xx.x%) |
| PT1   | x (xx.x%)          | x (xx.x%) | x (xx.x%)        | x (xx.x%) | x (xx.x%)      | x (xx.x%) |

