| PT2   | x (xx.x%)          | x (xx.x%) | x (xx.x%)        | x (xx.x%) | x (xx.x%)      | x (xx.x%) |
| ....  | x (xx.x%)          | x (xx.x%) | x (xx.x%)        | x (xx.x%) | x (xx.x%)      | x (xx.x%) |
| PTx   | x (xx.x%)          | x (xx.x%) | x (xx.x%)        | x (xx.x%) | x (xx.x%)      | x (xx.x%) |

\*Related: includes possibly, probably and definitely related

Note: Percentages are based on the number of subjects in each group.

**Table 14.3.1-6 Incidence of adverse events suspected to be related to study drug, by primary system organ class, preferred term and treatment**

Safety Set

| System Organ Class (SOC)
Preferred Term (PT) | Intensive
(N=X)    |              | Relaxed
(N=X)      |              | Total
(N=X)        |              |
|---|-----------------------|--------------|-----------------------|--------------|-----------------------|--------------|
|   | Nr (%) of
Subjects | Nr of
AEs | Nr (%) of
Subjects | Nr of
AEs | Nr (%) of
Subjects | Nr of
AEs |
| All Body Systems                                | x (xx.x%)             | x            | x (xx.x%)             | x            | x (xx.x%)             | x            |
| SOC1  | x (xx.x%)             | x            | x (xx.x%)             | x            | x (xx.x%)             | x            |
| PT1   | x (xx.x%)             | x            | x (xx.x%)             | x            | x (xx.x%)             | x            |
| PT2   | x (xx.x%)             | x            | x (xx.x%)             | x            | x (xx.x%)             | x            |
| ....  | ....                  | ....         | ....                  | ....         | ....                  | ....         |
| PTx   | x (xx.x%)             | x            | x (xx.x%)             | x            | x (xx.x%)             | x            |
| SOC2  | x (xx.x%)             | x            | x (xx.x%)             | x            | x (xx.x%)             | x            |
| PT1   | x (xx.x%)             | x            | x (xx.x%)             | x            | x (xx.x%)             | x            |
| PT2   | x (xx.x%)             | x            | x (xx.x%)             | x            | x (xx.x%)             | x            |
| ....  | ....                  | ....         | ....                  | ....         | ....                  | ....         |
| PTx   | x (xx.x%)             | x            | x (xx.x%)             | x            | x (xx.x%)             | x            |

.....  
AE: Adverse Event

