**Listing 16.2.7-3 Adverse events suspect to be related to study drug and/or ocular injection**

**Safety Set**

| Subject Number   | AE No | Adverse Event (REPORTED / Preferred / System Organ Class) | Start Date (YYYY-MM-DD) / Study Day | Stop Date (YYYY-MM-DD) / Study Day | Duration | Site       | Severity | Action Taken |
|------------------|-------|---|-------------------------------------|------------------------------------|----------|------------|----------|--------------|
| Intensive |       |   |                                     |                                    |          |            |          |              |
| XXX-XX           | X     | ABCD  | YYYY-MM-DD / X                      | YYYY-MM-DD / X                     | X        | Left       | Mild     | ABCD         |
| XXX-XX           | X     | ABCD  | YYYY-MM-DD / X                      | YYYY-MM-DD / X                     | X        | Right      | Mod      | ABCD         |
| XXX-XX           | X     | ABCD  | YYYY-MM-DD / X                      | YYYY-MM-DD / X                     | X        | Both       | Sev      | ABCD         |
| XXX-XX           | X     | ABCD  | YYYY-MM-DD / X                      | YYYY-MM-DD / X                     | X        | Non-Ocular | Mild     | ABCD         |
| Intensive |       |   |                                     |                                    |          |            |          |              |
| XXX-XX           | X     | ABCD  | YYYY-MM-DD / X                      | YYYY-MM-DD / X                     | X        | Left       | Mild     | ABCD         |
| XXX-XX           | X     | ABCD  | YYYY-MM-DD / X                      | YYYY-MM-DD / X                     | X        | Right      | Mod      | ABCD         |
| XXX-XX           | X     | ABCD  | YYYY-MM-DD / X                      | YYYY-MM-DD / X                     | X        | Both       | Sev      | ABCD         |

NK: Not Known; AE No = Adverse Number

Severity: Mild=Mild, Mod=Moderate, Sev=Severe

Action taken: 1=Study drug dosage adjusted/temporarily interrupted, 2=Study drug permanently discontinued due to this AE

3=Concomitant medication taken, 4=Non-drug therapy given, 5=Hospitalization/Prolonged hospitalization

Note: Day is relative to the first day of treatment (day 1)

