2.4.2 Study observation period

The study observation period for each patient will be defined as the period (in days) between the date of first treatment in the study eye (Day 1) and the date of the end of study visit + 1 (day).

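### The by-arm summaries of related adverse events use relationship to the study drug alone, while the plan's own related-event listing also covers the ocular injection

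*SAP*

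**What the plan says.** SAP section 2.9.1 plans five summaries of treatment-emergent adverse events, each done separately for ocular and non-ocular events. Only one concerns causality: "AEs suspected to be related to study drug". The same section promises that the per-patient listing will give the "suspected relationship (by the investigator) to the study drug / ocular injection, and eye (for ocular events", and among six listings it includes "Adverse events suspected to be related to study drug and/or ocular injection".

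The shells in the Protocol document repeat the split:

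- Table 14.3.1-5 is organised by "preferred term, maximum relationship to study drug and treatment".
- Table 14.3.1-6 is titled "Incidence of adverse events suspected to be related to study drug, by primary system organ class, preferred term and treatment", and Table 14.3.1-7 is its ocular counterpart.
- Listing 16.2.7-3 is titled "Adverse events suspect to be related to study drug and/or ocular injection".

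**The concern.** The plan recognises the injection as a possible cause distinct from the drug, but carries that cause only into a patient listing. Listings are read case by case; arms are compared in tables. As written, no table shows by arm the events that investigators attributed to the injection.

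In this trial that is an awkward category to leave out. Both arms receive ranibizumab and share the first three treatments at four-week intervals. The legend to the study design figure in the SAP introduction then says that intervals depend on arm and disease activity. The number of injections is a key secondary variable (SAP 2.8.1), with a between-arm ratio of injection frequency (SAP 2.8.2.7). The plan therefore compares how often each arm is injected without a matching comparison of the harms put down to injecting, which is part of weighing a relaxed regimen against an intensive one.

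**Working it through.** No arithmetic applies: the point depends on no rate, power, margin or standard deviation. The check is to see which attribution each planned output uses.

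| Output | Attribution used | By-arm comparison? |
|---|---|---|
| SAP 2.9.1, related-event summary | Drug | Yes |
| Table 14.3.1-5 | Drug | Yes |
| Table 14.3.1-6 | Drug | Yes |
| Table 14.3.1-7 (ocular) | Drug | Yes |
| Tables 14.3.1-1, -2, -8, -9 | None (any relationship) | Yes |
| Listings 16.2.7-1, -2, -4, -5, -6 | One column, drug | No |
| Listing 16.2.7-3 | Drug or injection, or both | No |

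So 3 of 3 relationship-based tables use the drug alone, 0 tables use the injection, and 1 listing uses either cause.

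Now follow three kinds of event through these outputs, supposing that drug and injection are recorded as two items:

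1. Suspected for the drug only: counted as related in Tables 14.3.1-5, -6 and -7 (the last if ocular), and listed in 16.2.7-3.
2. Suspected for both: the same. Nothing is lost.
3. Suspected for the injection only: listed in 16.2.7-3, falls in the not-suspected column of Table 14.3.1-5, and is absent from Tables 14.3.1-6 and -7. It is counted in Table 14.3.1-1, in -2 if ocular and in -8 or -9 if serious, with nothing to mark it as injection-related.

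Only the third kind is affected, and only if the two items exist. The wording of the related-event listing, which allows either cause or both, suggests that they do. The shells do not settle it. Five of the six adverse event listings carry a single relationship column, for the drug, and Listing 16.2.7-3 has no relationship column at all. Whichever way the data were collected, the listings as drawn do not deliver the drug and injection attribution that SAP 2.9.1 promises.

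**The case against.** The strongest reply is that the eCRF is not in the documents. If it holds one combined item, 'study drug' in the table titles is shorthand, Tables 14.3.1-5 to -7 already contain injection-related events, and only the label is wrong. This stands as a limit on the claim. It does not remove the mismatch, because one variable would then have different names in the tables and in the listing.

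Second, events put down to the injection are not missing from comparative output. They are counted by arm, with subjects and numbers of events, in the tables regardless of relationship, and also by severity, withdrawal, interruption and additional therapy. This stands too. A reader might infer that a real excess on one arm would be reported as no difference. The documents do not support that: an excess of ocular events would show in Table 14.3.1-2 without relying on investigator attribution. What is missing is the means of identifying those events as injection-related.

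Third, a reader might infer that the arms differ only in how often the eye is injected. They are defined by a fluid criterion for the interval decision (Table 14.2-7, footnote), and the relaxed arm tolerates some sub-retinal fluid. Injection frequency is the main way in which that criterion acts on the treatment delivered. Likewise, the 4-to-12-week range of intervals (12/4 = 3) might be read as a threefold difference in exposure. It is a range between patients; both arms may use any of these intervals, so it says nothing about the size of the arm difference.

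Last, SAP 2.9.1 times onset from the first treatment and again from Day 1, which SAP 2.4.2 makes the same date. It is tempting to ask for days since the latest injection instead. The redundancy is real, but the replacement is debatable: the arm injected more often has shorter times by construction, even for unrelated events, and the interval can be derived from the dates in Listings 16.2.5-1 and 16.2.7-1.

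**Conclusion.** The mismatch is confirmed by the text of SAP 2.9.1 and by the shells. Followed as written, the plan produces no by-arm table of events attributed to the injection, while its own listing treats them as related. Whether this omits events from the related-event tables or only mislabels those tables depends on whether the eCRF records the two attributions separately; the plan's wording suggests that it does, but this is an assumption.

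The size in events cannot be stated. The documents give neither event counts nor the share attributed to the injection alone, so it would be too strong to say that a whole category is known to be lost. Primary efficacy is untouched, and the events stay in the tables regardless of relationship. The point is a modest, inexpensive improvement to the safety reporting, worthwhile because injection frequency is the main difference in treatment delivered after the initial phase.

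**What to change.** In SAP 2.9.1 and in Tables 14.3.1-5, -6 and -7, define a related event as one suspected to be related to the drug, to the ocular injection, or to both, so that the tables match Listing 16.2.7-3. Where the eCRF records the two separately, show drug and injection attribution separately in those tables, and show both in the adverse event listings, including a column in Listing 16.2.7-3 for which cause was suspected. If the eCRF has one combined item, state this in SAP 2.9.1 and relabel the tables and the relationship columns accordingly.

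The cost is SAP wording and programming, on data that SAP 2.9.1 already says will be listed. The downside is that reported related-event rates may be somewhat higher; showing the drug attribution separately would keep the narrower figure available.
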